6.2 Withholding/Resuming Therapy

Study therapy will be withheld for the following adverse reactions:

a. A drug-related clinically significant toxicity \geq Grade 2, with the exception of the adverse reactions listed under requirement of permanent discontinuation of study therapy.

b. Grade 2 fatigue does not require the withholding of pembrolizumab.

c. When toxicity resolves or improves to \leq grade 1, therapy with pembrolizumab will resume.

d. In case toxicity does not resolve or improve to \leq grade 1 within 12 weeks after last administration of pembrolizumab, study drug discontinuation should be considered after discussion with SARC and overall study PI. If SARC, study PI and Merck are in agreement, patients who still have grade 2 toxicity at 12 weeks may continue on study only if asymptomatic and controlled.

e. Two dosing delays due to toxicity will be permitted. In the event of a third occurrence of a toxicity, which would require dosing delay, study therapy will be discontinued permanently.

f. For signs or symptoms of SJS or TEN, withhold KEYTRUDA® and refer the patient for specialized care for assessment and treatment.

Dose modification and toxicity management for immune-related AEs associated with pembrolizumab

AEs associated with pembrolizumab exposure may represent an immunologic etiology. These immune-related AEs (irAEs) may occur shortly after the first dose or several months after the last dose of pembrolizumab treatment and may affect more than on body system simultaneously. Therefore, early recognition and initiation of treatment is critical to reduce complications. Based on existing clinical trial data, most irAEs were reversible and could be managed with interruptions of pembrolizumab, administration of corticosteroids and/or other supportive care.

For suspected irAEs, ensure adequate evaluation to confirm etiology or exclude other causes. Additional procedures or tests such as bronchoscopy, endoscopy, skin biopsy may be included as part of the evaluation. Based on the severity of irAEs, withhold or permanently discontinue pembrolizumab and administer corticosteroids. Dose modification and toxicity management guidelines for irAEs associated with pembrolizumab are provided in Table 4.

Table 4: Dose Modification and Toxicity Management Guidelines for Immune-related AEs Associated with Pembrolizumab

General instructions:

- 1. Corticosteroid taper should be initiated upon AE improving to Grade 1 or less and continue to taper over at least 4 weeks.
- 2. For situations where pembrolizumab has been withheld, pembrolizumab can be resumed after AE has been reduced to Grade 1 or 0 and corticosteroid has been tapered. Pembrolizumab should be permanently discontinued if AE does not resolve within 12 weeks of last dose or corticosteroids cannot be reduced to ≤ 10 mg prednisone or equivalent per day within 12 weeks.
- **3.** For severe and life-threatening irAEs, IV corticosteroid should be initiated first followed by oral steroid. Other immunosuppressive treatment should be initiated if irAEs cannot be controlled by corticosteroids.

| Immune-related AEs | Toxicity grade or conditions (CTCAEv4.0) | Action taken to pembrolizumab | irAE management with corticosteroid and/or other therapies | Monitor and follow- up |
|-----------------------|--|----------------------------------|---|---|
| Pneumonitis | Grade 2 Grade 3 or 4, or recurrent Grade 2 | Withhold Permanently discontinue | • Administer corticosteroids (initial dose of 1-2 mg/kg prednisone or equivalent) followed by taper | Monitor participants for signs and symptoms of pneumonitis Evaluate participants with suspected pneumonitis with radiographic imaging and initiate corticosteroid treatment Add prophylactic antibiotics for opportunistic infections |
| Diarrhea / Colitis | Grade 2 or 3 | Withhold | • Administer corticosteroids (initial dose of 1-2 mg/kg prednisone or equivalent) followed by taper | • Monitor participants for signs and symptoms of enterocolitis (ie, diarrhea, |

| Immune-related AEs | Toxicity grade or conditions (CTCAEv4.0) | Action taken to pembrolizumab | irAE management with corticosteroid and/or other therapies | Monitor and follow- up |
|---|---|----------------------------------|---|--|
| | Grade 4 | Permanently discontinue | | abdominal pain, blood or mucus in stool with or without fever) and of bowel perforation (ie, peritoneal signs and ileus). Participants with ≥ Grade 2 diarrhea suspecting colitis should consider GI consultation and performing endoscopy to rule out colitis. Participants with diarrhea/colitis should be advised to drink liberal quantities of clear fluids. If sufficient oral fluid intake is not feasible, fluid and electrolytes should be substituted via IV infusion. |
| AST / ALT elevation or Increased | Grade 2 | Withhold | Administer corticosteroids (initial dose of 0.5- 1 mg/kg prednisone or equivalent) followed by taper | • Monitor with liver function tests (consider |
| bilirubin | Grade 3 or 4 | Permanently discontinue | • Administer corticosteroids (initial dose of 1-2 mg/kg prednisone or equivalent) followed by taper | weekly or more frequently until liver enzyme value returned to baseline or is stable |
| Type 1 diabetes mellitus (T1DM) or Hyperglycemia | Newly onset T1DM or Grade 3 or 4 hyperglycemia associated with evidence of β-cell failure | Withhold | Initiate insulin replacement therapy for participants with T1DM Administer anti-hyperglycemic in participants with hyperglycemia | • Monitor participants for hyperglycemia or other signs and symptoms of diabetes. |
| Hypophysitis | Grade 2 | Withhold | | • Monitor for signs and symptoms of |

| Immune-related AEs | Toxicity grade or conditions (CTCAEv4.0) | Action taken to pembrolizumab | irAE management with corticosteroid and/or other therapies | Monitor and follow- up |
|-----------------------------|--|--|---|--|
| | Grade 3 or 4 | Withhold or permanently discontinue ¹ | Administer corticosteroids and initiate hormonal replacements as clinically indicated. | hypophysitis (including hypopituitarism and adrenal insufficiency) |
| Hyperthyroidism | Grade 2 | Continue | • Treat with non-selective beta- blockers (eg, propranolol) or thionamides as appropriate | Monitor for signs and symptoms of thyroid |
| | Grade 3 or 4 | Withhold or permanently discontinue ¹ | | disorders. |
| Hypothyroidism | Grade 2-4 | Continue | • Initiate thyroid replacement hormones (eg, levothyroxine or liothyroinine) per standard of care | Monitor for signs and symptoms of thyroid disorders. |
| Nephritis and Renal | Grade 2 | Withhold | Administer corticosteroids (prednisone 1-2 mg/kg or | • Monitor changes of renal function |
| dysfunction | Grade 3 or 4 | Permanently discontinue | equivalent) followed by taper. | |
| Myocarditis | Grade 1 or 2 | Withhold | Based on severity of AE administer corticosteroids | • Ensure adequate evaluation to |
| | Grade 3 or 4 | Permanently discontinue | | confirm etiology and/or exclude other causes |
| All other immune-related | Intolerable/ persistent Grade 2 | Withhold | • Based on type and severity of AE administer corticosteroids | • Ensure adequate evaluation to |
| AEs | Grade 3 Grade 4 or recurrent Grade 3 | Withhold or discontinue based on the type of event. Events that require discontinuation include and not limited to: Gullain-Barre Syndrome, encephalitis Permanently discontinue | | confirm etiology and/or exclude other causes |

NOTE:

For participants with Grade 3 or 4 immune-related endocrinopathy where withhold of pembrolizumab is required, pembrolizumab may be resumed when AE resolves to \leq Grade 2 and is controlled with hormonal replacement therapy or achieved metabolic control (in case of T1DM).

Guidelines for Infusion Reactions

Dose modification and toxicity management of infusion-reactions related to pembrolizumab

Pembrolizumab may cause severe or life threatening infusion-reactions including severe hypersensitivity or anaphylaxis. Signs and symptoms usually develop during or shortly after drug infusion and generally resolve completely within 24 hours of completion of infusion. Dose modification and toxicity management guidelines on pembrolizumab associated infusion reaction are provided in Table 5.

| Mild reaction; infusion interruption not indicated; intervention not indicatedindic stableGrade 2Stop Requires therapy or infusion interruption but responds promptly to symptomatic treatment (e.g., antihistamines, NSAIDs, narcotics, IV fluids); prophylactic medications indicated for ≤ 24 hrsNSA NSAID infusion infusion infusion indicated fluids); prophylactic medications indicated for ≤ 24 hrsIntervention indicated infusion infusion infusion infusion infusion infusion indicated for ≤ 24 hrsStop indicated infusion <b< th="">rease monitoring of vital signs as medically icated until the subject is deemed medically ble in the opinion of the investigator. p Infusion. ditional appropriate medical therapy may lude but is not limited to: fluids tihistamines AIDs etaminophen rcotics rease monitoring of vital signs as medically icated until the subject is deemed medically ble in the opinion of the investigator. symptoms resolve within 1 hour of stopping drug usion, the infusion may be restarted at 50% of original infusion rate (e.g. from 100 mL/hr to 50 ./hr). Otherwise dosing will be held until nptoms resolve and the subject should be	None Subject may be premedicated 1.5h (± 30 minutes) prior to infusion ofwith: Diphenhydramine 50 mg po (or equivalent dose of antihistamine). Acetaminophen 500-1000 mg po (or equivalent dose of analgesic).	</b<> | rease monitoring of vital signs as medically icated until the subject is deemed medically ble in the opinion of the investigator. p Infusion. ditional appropriate medical therapy may lude but is not limited to: fluids tihistamines AIDs etaminophen rcotics rease monitoring of vital signs as medically icated until the subject is deemed medically ble in the opinion of the investigator. symptoms resolve within 1 hour of stopping drug usion, the infusion may be restarted at 50% of original infusion rate (e.g. from 100 mL/hr to 50 ./hr). Otherwise dosing will be held until nptoms resolve and the subject should be | None Subject may be premedicated 1.5h (± 30 minutes) prior to infusion ofwith: Diphenhydramine 50 mg po (or equivalent dose of antihistamine). Acetaminophen 500-1000 mg po (or equivalent dose of analgesic). |
|---|---|---|
| Grade 2StopRequires therapy orAddinfusion interruption butincluicresponds promptly toIV fsymptomatic treatmentAntii(e.g., antihistamines,NSANSAIDs, narcotics, IVAcetfluids); prophylacticNarcoticsmedications indicatedIncredingfor ≤ 24 hrsindicesymptomaticstableIf syinfusiongrades 3 or 4StopGrades 3 or 4StopGrade 3:AddProlonged (i.e., notincluicand/or brief interruptionAntii | ditional appropriate medical therapy may lude but is not limited to: fluids tihistamines AIDs etaminophen rcotics rease monitoring of vital signs as medically icated until the subject is deemed medically ble in the opinion of the investigator. ymptoms resolve within 1 hour of stopping drug usion, the infusion may be restarted at 50% of original infusion rate (e.g. from 100 mL/hr to 50 ./hr). Otherwise dosing will be held until nptoms resolve and the subject should be | 1.5h (± 30 minutes) prior to infusion of with: Diphenhydramine 50 mg po (or equivalent dose of antihistamine). Acetaminophen 500-1000 mg po (or equivalent dose of |
| Requires therapy or infusion interruption but responds promptly to symptomatic treatment (e.g., antihistamines, NSAIDs, narcotics, IV fluids); prophylactic medications indicated for ≤ 24 hrsAcet indic indic stable If sy infus the c mL/ symp pren Sub adec discGrades 3 or 4 Grade 3: Prolonged (i.e., not rapidly responsive to symptomatic medication It enterruptionAdd inch inch stable If sy infus the c mL/ symptomatic mode of the symptomatic medication inch rapidly responsive to and/or brief interruptionAdd inch inch symptomatic medication inch <br< td="">ditional appropriate medical therapy may lude but is not limited to: fluids tihistamines AIDs etaminophen rcotics rease monitoring of vital signs as medically icated until the subject is deemed medically ble in the opinion of the investigator. ymptoms resolve within 1 hour of stopping drug usion, the infusion may be restarted at 50% of original infusion rate (e.g. from 100 mL/hr to 50 ./hr). Otherwise dosing will be held until nptoms resolve and the subject should be

	1.5h (± 30 minutes) prior to infusion of with: Diphenhydramine 50 mg po (or equivalent dose of antihistamine). Acetaminophen 500-1000 mg po (or equivalent dose of

	</br<> | ditional appropriate medical therapy may lude but is not limited to: fluids tihistamines AIDs etaminophen rcotics | 1.5h (± 30 minutes) prior to |
| Grade 3:AddProlonged (i.e., notinclurapidly responsive toEpirsymptomatic medicationIV fand/or brief interruptionAnti | medicated for the next scheduled dose. bjects who develop Grade 2 toxicity despite equate premedication should be permanently continued from further study drug treatment | |
| Prolonged (i.e., notinclurapidly responsive toEpirsymptomatic medicationIV fand/or brief interruptionAnti | p Infusion. | No subsequent dosing |
| of symptoms following initial improvement; Narc hospitalization indicated for other clinical Press sequelae (e.g., renal Cort impairment, pulmonary infiltrates) Incro Grade 4: Stabl Life-threatening; pressor or ventilatory support **In indicated used | ditional appropriate medical therapy may lude but is not limited to: inephrine** fluids tihistamines AIDs etaminophen rcotics ygen essors rticosteroids rease monitoring of vital signs as medically icated until the subject is deemed medically ble in the opinion of the investigator. spitalization may be indicated. n cases of anaphylaxis, epinephrine should be d immediately. bject is permanently discontinued from | |

Table 5: Pembrolizumab Infusion Reaction Dose modification and Treatment Guidelines

Confidential Protocol SARC028 v 5.0: 18OCT2019 Copyright©SARC (Sarcoma Alliance for Research through Collaboration)

Other allowed dose interruption for pembrolizumab

Pembrolizumab may be interrupted for situations other than treatment-related AEs such as medical / surgical events or logistical reasons not related to study therapy. Subjects should be placed back on study therapy within 3 weeks of the scheduled interruption, unless otherwise discussed with the Sponsor. The reason for interruption should be documented in the patient's study record.

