5.4.1.1 Prohibited Concomitant Medications

Patients are prohibited from receiving the following therapies during the Screening and Treatment Phase (including retreatment for post-complete response relapse) of this trial:

- Anti-cancer systemic chemotherapy or biological therapy
- Immunotherapy not specified in this protocol
- Chemotherapy not specified in this protocol
- Investigational agents other than pembrolizumab
- Radiation therapy
 - Note: Radiation therapy to a symptomatic solitary lesion or to the brain may be allowed after consultation with Sponsor.
- Live vaccines within 30 days prior to the first dose of study drug and while on study. Examples of live vaccines include, but are not limited to the following: measles, mumps, rubella, chicken pox, yellow fever, rabies, BCG, and typhoid (oral) vaccine. Seasonal influenza vaccines for injection are generally killed virus vaccines and are allowed; however intranasal influenza vaccines (e.g. Flu-Mist®) are live attenuated vaccines, and are not allowed.
- Glucocorticoids for any purpose other than to treat or prevent any AE, or to modulate symptoms from an event of clinical interest of suspected immunologic etiology. The use of physiologic dose of corticosteroids is allowed.

Patients who require the use of any of the aforementioned treatments for clinical management, per the site Investigator's assessment should be removed from the trial. Patients may receive other medications that the investigator deems to be medically necessary.

The Exclusion Criteria describes other medications which are prohibited in this trial.

There are no prohibited therapies during the Post-Treatment Follow-up Phase.

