5.4.2 Rescue Medications & Supportive Care

5.4.2.1 Supportive Care Guidelines

Patients should receive appropriate supportive care measures as deemed necessary by the treating site Investigator including but not limited to the items outlined below:

Pneumonitis:

• For **Grade 2 events**, treat with systemic corticosteroids (1-2 mg/kg/day of prednisone or equivalent).

- For Grade 3-4 events, bronchoscopy should be performed to exclude infectious etiologies before starting immunosuppression. Once infectious etiologies are excluded, immediately treat with intravenous steroids (1-2 mg/kg/day of prednisone or equivalent). If symptoms persist for more than 3-5 days, then begin infliximab 5 mg/kg. When symptoms improve to Grade 1 or less, steroid taper should be started and continued over no less than 4 weeks. Permanently discontinue pembrolizumab.
- When symptoms improve to Grade 1 or less, steroid taper should be started and continued over no less than 4 weeks. Permanently discontinue pembrolizumab.
- Add prophylactic antibiotics for opportunistic infections in the case of prolonged steroid administration.

Diarrhea/Colitis:

Subjects should be carefully monitored for signs and symptoms of enterocolitis (such as diarrhea, abdominal pain, blood or mucus in stool, with or without fever) and of bowel perforation (such as peritoneal signs and ileus).

- All subjects who experience diarrhea/colitis should be advised to drink liberal quantities of clear fluids. If sufficient oral fluid intake is not feasible, fluid and electrolytes should be substituted via IV infusion. For Grade 2 or higher diarrhea, consider GI consultation and endoscopy to confirm or rule out colitis.
- For **Grade 2 diarrhea/colitis**, administer oral corticosteroids (1-2 mg/kg/day prednisone or equivalent).
- For **Grade 3 or 4 diarrhea/colitis,** treat with intravenous steroids (1-2 mg/kg/day prednisone or equivalent) followed by high dose oral steroids. If grade 3-4 diarrhea persists for more than 3-5 days, then begin infliximab 5 mg/kg.
 - For grade 4 diarrhea/colitis, permanently discontinue pembrolizumab.
- When symptoms improve to Grade 1 or less, steroid taper should be started and continued over no less than 4 weeks.

Type 1 diabetes mellitus (if new onset, including diabetic ketoacidosis [DKA]) or ≥ Grade 3 Hyperglycemia, if associated with ketosis (ketonuria) or metabolic acidosis (DKA)

- For **T1DM** or **Grade 3-4** Hyperglycemia

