 - Insulin replacement therapy is recommended for Type I diabetes mellitus and for Grade 3-4 hyperglycemia associated with

metabolic acidosis or ketonuria.

• Evaluate patients with serum glucose and a metabolic panel, urine ketones, glycosylated hemoglobin, and C-peptide.

Hypophysitis:

- For **Grade 2** events, treat with corticosteroids (1-2 mg/kg/day prednisone or equivalent). When symptoms improve to Grade 1 or less, steroid taper should be started and continued over no less than 4 weeks. Replacement of appropriate hormones may be required as the steroid dose is tapered.
- For **Grade 3-4** events, treat with an initial dose of IV corticosteroids followed by oral corticosteroids. When symptoms improve to Grade 1 or less, steroid taper should be started and continued over no less than 4 weeks. Replacement of appropriate hormones may be required as the steroid dose is tapered.

Hyperthyroidism or Hypothyroidism:

Thyroid disorders can occur at any time during treatment. Monitor patients for changes in thyroid function (at the start of treatment, periodically during treatment, and as indicated based on clinical evaluation) and for clinical signs and symptoms of thyroid disorders.

- Grade 2 hyperthyroidism events (and Grade 2-4 hypothyroidism):
 - In hyperthyroidism, non-selective beta-blockers (e.g. propranolol) are suggested as initial therapy.
 - In hypothyroidism, thyroid hormone replacement therapy, with levothyroxine or liothyronine, is indicated per standard of care.
- Grade 3-4 hyperthyroidism
 - Treat with an initial dose of IV corticosteroid followed by oral corticosteroids (1-2 mg/kg/day prednisone or equivalent). When symptoms improve to Grade 1 or less, steroid taper should be started and continued over no less than 4 weeks. Replacement of appropriate hormones may be required as the steroid dose is tapered.
 - Permanently discontinue pembrolizumab for **Grade 4** hyperthyroidism.

Hepatic Adverse Events:

- For **Grade 2** events, monitor liver function tests more frequently until returned to baseline values (consider weekly).
 - Treat with IV or oral corticosteroids (0.5-1 mg/kg/day prednisone or equivalent)
- For Grade 3-4 events, treat with intravenous corticosteroids for 24 to

48 hours (1-2 mg/kg/day prednisone or equivalent. If grade 3-4 hepatitis persists for more than 3-5 days, then begin mycophenolate 1 g twice daily. Permanently discontinue pembrolizumab for AST or ALT > 5x ULN or total bilirubin >3x ULN.

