6. DOSING DELAYS/DOSE MODIFICATIONS

Dose reduction of pembrolizumab will not be permitted in individual patients.

6.1 Discontinuation of Therapy:

Therapy with pembrolizumab will be permanently discontinued for any of the following:

a. Severe or life-threatening adverse reactions, including, but not limited to, any of the following (SARC must be notified in the event of these AEs and final decision regarding treatment will be made after a discussion):

- Drug related grade 4 toxicity (non-hematologic or hematologic)
- Diarrhea with abdominal pain, fever, ileus, or peritoneal signs; increase in stool frequency (7 or more bowel movements over baseline), stool incontinence, need for intravenous hydration for more than 24 hours, gastrointestinal hemorrhage, and gastrointestinal perforation
- Aspartate aminotransferase (AST) or alanine aminotransferase (ALT) >5 times upper limit of normal. For patients with liver metastasis who entered the study with grade 2 elevation of AST/ALT, pembrolizumab will be permanently discontinued if AST/ALT increase ≥ 50% relative to baseline and lasting ≥ 1 week)
- Total serum bilirubin >3 times upper limit of normal
- Severe (i.e., CTCAE grade 3 or 4) motor or sensory neuropathy, Guillain-Barré syndrome, or myasthenia gravis or other neurologic symptoms that impact activity of daily living
- Severe immune-mediated reactions involving any other organs (e.g., nephritis, pneumonitis, pancreatitis, non-infectious myocarditis)
- Immune-mediated ocular disease that is unresponsive to topical immunosuppressive therapy
- Grade 4 infusion reaction

• Confirmed diagnosis of Stevens-Johnson Syndrome (SJS) or Toxic Epidermal Necrolysis (TEN)

b. Inability to reduce corticosteroid dose for immune-related adverse reactions to ≤ 10 mg prednisone or equivalent per day

c. New or worsening ophthalmologic disorders, including loss of visual acuity or visual field and evidence of retinopathy.

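### Section 6.2c restarts pembrolizumab at grade 1 with no steroid condition, Table 4 also requires the corticosteroid taper, and no sentence says which rule prevails

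*Combined protocol and SAP*

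**What the plan says.** Section 6.2 opens with a lettered list on withholding and resuming. Item a withholds drug for clinically significant drug-related toxicity of grade 2 or more, except reactions listed for permanent discontinuation. Under item c, once toxicity is at or below "grade 1, therapy with pembrolizumab will resume". Item d covers toxicity that has not settled 12 weeks after the last dose. Stopping is then to be considered after discussion, and grade 2 toxicity that is asymptomatic and controlled may continue if SARC, the study PI and Merck agree. Item e allows two toxicity delays.

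A separate passage on immune-related events follows, still within 6.2. Its link to the table reads "Dose modification and toxicity management guidelines for irAEs associated with pembrolizumab are provided in Table 4". Table 4 begins with general instructions:

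- Instruction 1: "Corticosteroid taper should be initiated upon AE improving to Grade 1 or less and continue to taper over at least 4 weeks".
- Instruction 2, for drug that has been withheld: "pembrolizumab can be resumed after AE has been reduced to Grade 1 or 0 and corticosteroid has been tapered". The same instruction calls for permanent discontinuation if the event has not resolved within 12 weeks of the last dose, or if steroid cannot be brought to 10 mg/day of prednisone or less within 12 weeks.

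**The concern.** Two restart rules stand in one section, and for a steroid-treated immune-related event they point to different dates. Item c is triggered by grade alone and is worded as something that will happen. Table 4 needs the grade and the taper. Because the taper begins at grade 1, the moment that satisfies item c is the moment at which Table 4 starts the waiting period.

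At stake is a dose of a checkpoint inhibitor given while the patient is still being weaned off steroid for an organ toxicity attributed to that drug. Practice could also differ between the roughly 10 sites, each able to cite the protocol.

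**Working it through.** No statistical figure is involved. The check sets the texts side by side and adds one piece of arithmetic on the schedule.

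**Step 1. The restart rules**

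| | 6.2, item c | Table 4, instructions 1 and 2 |
|---|---|---|
| Toxicity covered | Any; no limit to non-immune events | Immune-related events |
| Grade needed | 1 or lower | 0 or 1 |
| Steroid condition | None | Taper done; starts at grade 1 or less, at least 4 weeks |
| Force | Drug will resume | Drug can be resumed |

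**Step 2. Does any sentence rank them?** The link to Table 4 says where the immune-related guidelines are. It does not say that they replace items a to e, and those items are not confined to other toxicities.

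**Step 3. Does another steroid rule block re-dosing mid-taper?** Two candidates exist, and neither does.

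- Section 5.4.1.1 prohibits "Glucocorticoids for any purpose other than to treat or prevent any AE", so steroid given to treat an adverse event is allowed during treatment.
- Section 6.1, item b, lists "Inability to reduce corticosteroid dose for immune-related adverse reactions" to 10 mg/day or less. That is a reason to stop for good, not a condition for restarting.

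**Step 4. Which events are exposed?** They are events that Table 4 withholds, and does not stop, and that are treated with steroid:

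- Grade 2 pneumonitis, colitis and nephritis: 1-2 mg/kg.
- Grade 2 hepatic events: 0.5-1 mg/kg.
- Grade 2 hypophysitis: withheld in Table 4; section 5.4.2.1 gives 1-2 mg/kg and a taper of at least 4 weeks.

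Section 5.4.2.1 also has a pneumonitis bullet, with no grade attached, that ends in permanent discontinuation. I follow Table 4, which withholds at grade 2. Table 4 stops grade 3-4 pneumonitis, nephritis and hepatic events permanently, so item c does not reach them. Table 4 withholds grade 3 colitis, but diarrhea of 7 or more movements over baseline is on the 6.1a discontinuation list, which item a excludes. The colitis at issue is therefore chiefly grade 2.

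**Step 5. Size in scheduled doses.** Inputs: minimum taper 4 weeks = 28 days (instruction 1); dosing interval 3 weeks = 21 days (section 5.1).

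28 / 21 = 1.33 cycles

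A 28-day window is longer than one interval, so it contains at least one scheduled dosing day wherever it starts. This assumes that tapered means finished and that the 21-day visit grid runs on through the hold. If tapered means only reduced to some dose, the gap is shorter, and the documents do not say by how much.

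**Step 6. The 12-week rules.** For an immune-related event still at grade 2, asymptomatic and controlled 12 weeks after the last dose, item d permits continuation by three-party agreement. Instruction 2 says to discontinue permanently. The defaults differ, and neither rule mentions the other.

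**Step 7. Thyroid events.** Table 4 continues drug for grade 2 hyperthyroidism and grade 2-4 hypothyroidism. Item a could be read as requiring a hold, since item b exempts only grade 2 fatigue. Such a hold could use up one of the two delays in item e and section 5.6.

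**The case against.** The best defence is that the protocol already contains the right rule in the right place. Table 4 lies within 6.2, under its own heading for immune-related events, and instruction 2 speaks directly to drug that has been withheld. Item c does not say that drug restarts immediately, so a site can satisfy both by treating item c as the grade criterion and Table 4 as an added condition. Biweekly site calls (section 12.2) and monthly committee review (section 12.1.2) could catch a divergent practice.

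Most of this stands, and it limits the point. A reader might infer that sites have no steroid rule for immune-related events. The documents do not support that: the rule is in Table 4, and what is missing is the sentence giving it precedence. That the specific rule outranks the general one remains an inference, however, set against an item worded as mandatory. Calls and committee review work after the fact.

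A reader might also infer that items a to e conflict with Table 4 throughout. They do not. Item b raises no conflict. On item e, Table 4 only adds an earlier stop for some recurrences, such as recurrent grade 2 pneumonitis. The thyroid difference is softened because item a is limited to clinically significant toxicity. Section 6.1a lists drug-related grade 4 toxicity, while Table 4 continues grade 4 hypothyroidism, but 6.1a leaves the final decision to a discussion with SARC. The item d exception needs agreement from SARC, the study PI and Merck, so sites cannot diverge on it alone.

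**Conclusion.** The inconsistency is real and should be corrected. Followed literally, item c restarts drug at the start of a taper that Table 4 requires first, and nothing else in the protocol prevents this. The size is at least one scheduled dose per affected event, on the two assumptions in the schedule arithmetic. The 12-week difference is a second, smaller inconsistency; the thyroid point needs only a clarification.

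Two stronger readings are not supported. One might try to state how much steroid a patient would still be taking at the next dose. That needs body weights and a taper shape, and the documents give neither. One might also suspect an effect on the efficacy result. The text gives no basis for one: the ORR definition and the success rule of 8 responses in 40 do not depend on which restart rule applies.

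**What to change.** - State in 6.2 that, for immune-related adverse events, Table 4 and its instructions prevail over items a, c and d, without relaxing the 6.1 stopping rules or the duty to notify SARC.
- Add to item c that any corticosteroid given for the event must have been tapered as in Table 4. The sponsor should say whether this means finished, or at or below a set dose. Adopting 10 mg/day by default is not advisable: if finished was intended, that limit would loosen Table 4.
- Say whether the agreement in item d is an exception to the 12-week stop in instruction 2.
- Say that thyroid events for which Table 4 continues drug need no hold under item a, and so do not count as delays under item e or section 5.6.

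The cost is an amendment to the wording of 6.2 and Table 4, a cross-reference in 5.6, and a memo to sites. No extra visits, tests or patients are needed.
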